## SAP Amendments before database lock

Version	Issue Date	Section	Revision / Addition	Rationale

QMD Ref: Worldwide-TMP-ST-006-4.0 Effective: 12Aug2019	Governing QMD: Worldwide-SOP-ST-001
Confidentiality Statement	

This document is the property of Worldwide Clinical Trials Inc. and may not be duplicated, copied, altered or removed from company without prior approval from Worldwide Quality Assurance or in compliance with Worldwide Standard Operating Procedures.

Worldwide Clinical Trials Controlled Quality Management Document			
 WORLDWIDE CLINICAL TRIALS	Sponsor:	Opiant Pharmaceuticals	Protocol Number:

	Protocol Number:	OPNT003-PK-001	

## 1 INTRODUCTION

This document details the planned statistical analyses for Opiant Pharmaceuticals, protocol “OPNT003-PK-001” study titled “A Two-Period, Two-Treatment, Randomized Crossover Study of the Pharmacokinetics of Nalmefene by Intranasal and Intramuscular Administration in Healthy Volunteers”.

The proposed analyses are based on the contents of the final version of the protocol (dated 11-NOV-2020) and the protocol clarification letter (dated 04-JAN-2021).

This will be an inpatient, open-label, randomized, 2-period, 2-treatment, 2 sequence, crossover study in healthy volunteers. Each subject will receive 2 treatments during the 2 dosing periods (1 treatment per dosing period):

Treatment A (Test)	3 mg nalmefene hydrochloride IN dose (one 0.1 mL spray of a 30 mg/mL solution in one nostril)
Treatment B (Reference)	1.0 mg nalmefene IM dose (1.0 mL of 1.108 mg/mL nalmefene hydrochloride solution as a single dose in the gluteal muscle)

## 2 STUDY OBJECTIVES

The primary objective is to

- Determine the pharmacokinetics (PK) of 3mg nalmefene hydrochloride IN compared to a 1.0 mg dose of nalmefene administered IM, to demonstrate systemic exposure comparable to an approved IM dose

The secondary objective is to

- Evaluate the safety and tolerability of IN nalmefene

## 3 ENDPOINTS

### 3.1 Pharmacokinetic Endpoints

The following plasma pharmacokinetic parameters for nalmefene will be calculated using non-compartmental analysis:

- Maximum plasma concentration ( $C_{max}$ )
- Time to maximum plasma concentration ( $T_{max}$ )

QMD Ref: Worldwide-TMP-ST-006-4.0 Effective: 12Aug2019	Governing QMD: Worldwide-SOP-ST-001
Confidentiality Statement	

This document is the property of Worldwide Clinical Trials Inc. and may not be duplicated, copied, altered or removed from company without prior approval from Worldwide Quality Assurance or in compliance with Worldwide Standard Operating Procedures.

Worldwide Clinical Trials Controlled Quality Management Document			
 WORLDWIDE CLINICAL TRIALS	Sponsor:	Opiant Pharmaceuticals	

- Area under the curve to the final time with a concentration equal to or greater than the lower limit of quantitation [AUC(0-t)], to infinity [AUC(inf)], and during the first 30 minutes [AUC0-2.5 mins, AUC0-5 mins, AUC0-10 mins, AUC0-15 mins, AUC0-20 mins and AUC0-30 mins]
- Terminal elimination rate constant ( $\lambda_z$ )
- Half-life ( $t_{1/2}$ )
- Clearance (CL/F)
- Volume of distribution (Vz/F) uncorrected for bioavailability (F)

### 3.2 Safety Endpoints

Safety endpoints will include:

- Adverse events (AEs)
- Vital signs (heart rate, sitting blood pressure, and respiration rate)
- Electrocardiogram (ECG)
- Clinical laboratory changes
- Numerical rating scale (NRS) measuring acute nasal pain and nasal irritation (erythema, edema, and erosion) determined from the nasal passage examination following each nasal administration of study drug

## 4 SAMPLE SIZE

This study is designed to obtain information regarding the PK of IN nalnefene under the conditions of this study. The number of subjects has been determined based on the data from the pilot study.

The sample size was based on Geometric Means Ratio (GMR) and Intrasubject Variability (ISCV) results obtained for partial AUC in the pilot study, covering the initial 30 minutes. Sample size calculations are based on the non-inferiority t-test for log-normal distributed data and were performed for study designs: 2x2x2 (2 treatments x 2 sequences x 2 periods), using a target power of 80% and alpha level of 5%.

Parameter	Total ISCV %	GMR %	Sample size estimation	Expected power
AUC 0-5 mins/Dose	178.15	149.40	48	81.0
AUC 0-10 mins/Dose	129.21	127.06	60	81.1
AUC 0-15 mins/Dose	159.69	108.76	168	80.1
AUC 0-20 mins/Dose	127.97	125.68	60	81.0
AUC 0-30 mins/Dose	74.40	123.57	32	81.5

QMD Ref: Worldwide-TMP-ST-006-4.0 Effective: 12Aug2019	Governing QMD: Worldwide-SOP-ST-001
Confidentiality Statement	

This document is the property of Worldwide Clinical Trials Inc. and may not be duplicated, copied, altered or removed from company without prior approval from Worldwide Quality Assurance or in compliance with Worldwide Standard Operating Procedures.

Worldwide Clinical Trials Controlled Quality Management Document			
 WORLDWIDE CLINICAL TRIALS	Sponsor:	Opiant Pharmaceuticals	
	Protocol Number:	OPNT003-PK-001	

Based on these findings a sample size of 60 subjects has been selected. For this study 68 subjects will be enrolled.

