AUC 0-30min	Area under the concentration–time curve from time-zero to 30 min; calculated using the linear trapezoidal rule allowing for extrapolation/interpolation to 30min
AUC last (AUC 0-t )	Area under the concentration–time curve from time-zero to the time of the last quantifiable concentration; calculated using the linear trapezoidal rule
AUC last/Dose	AUC last adjusted for the nominal administered dose
AUC inf	Area under the concentration–time curve extrapolated to infinity, calculated as: $AUC_{inf} = AUC_{last} + C_{last}/\lambda_z,$ where $C_{last}$ is the last quantifiable concentration and $\lambda_z$ is the terminal elimination rate constant. The percentage of AUC inf based on extrapolation should be <30.0%
AUC inf/Dose	AUC inf adjusted for the nominal administered dose
AUC% Extrap	The percentage of AUC inf based on extrapolation, calculated as: $\%AUC_{Extrap} = (AUC_{inf} - AUC_{last})/AUC_{inf} * 100$
$\lambda_z$	The observed elimination rate constant ( $\lambda_z$ ); estimated by linear regression in the terminal phase of the log concentration-time profile; see additional criteria below
T 1/2	The observed terminal elimination half-life calculated as: $T_{1/2} = \ln(2)/\lambda_z$
C last	The last quantifiable concentration, determined directly from individual concentration-time data
T last	Time of the last quantifiable concentration
CL/F	Apparent total body clearance after extravascular administration, calculated as: $CL/F = Dose/AUC_{inf}$
Vz/F	Apparent volume of distribution following extravascular administration based on the terminal phase, calculated as: $Vz/F = Dose/(AUC_{inf} * \lambda_z)$
Fre l	Ratio of dose-adjusted AUC inf following IN administration of the test product relative to dose-adjusted AUC inf following IM administration of the reference product

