## 6.11 PK Analyses

Blood samples for determination of plasma concentrations of nalmefene will be collected at:

Predose (0 h), and at 2.5, 5, 7.5, 10, 15, 20, 30, and 45 minutes and 1, 2, 3, 4, 6, 8, 12, 18, 24, 36, and 48 hours post dose.

Concentration-time data will be tabulated by nominal time, analyte, and treatment using descriptive statistics. For presentation of the individual data and summary statistics, concentrations below the limit of quantitation (BLQ) will be set to zero.

Individual subject and mean plasma concentration-time data will be presented graphically on linear and semi-logarithmic scales. Mean data will be plotted using nominal sample times, and individual data will be plotted using actual times.

PK parameters for nalmefene will be calculated as described in section 5.2.13.

PK parameters will be summarized by analyte and treatment using descriptive statistics.

Comparison of the log-transformed PK parameters  $C_{\max}$ ,  $AUC_{0-2.5\text{min}}$ ,  $AUC_{0-5\text{min}}$ ,  $AUC_{0-10\text{min}}$ ,  $AUC_{0-15\text{min}}$ ,  $AUC_{0-20\text{min}}$ , and  $AUC_{0-30\text{min}}$ ,  $AUC_{\text{last}}$ , and  $AUC_{\text{inf}}$  across treatments will be performed using an analysis of variance (ANOVA) model and the two one-sided t-tests procedure at the  $\alpha = 0.05$  level of significance. The model will include sequence, treatment, and period as fixed effects and subject nested within sequence as the random effect. The following comparison(s) will be made:

- Test Product (Treatment A) vs. Reference Product (Treatment B)

The ratios of the geometric means (Test / Reference) and 90% confidence intervals will be reported. The analysis will be performed in SAS using PROC GLM.

Conclusions regarding the results of the statistical analysis (ANOVA) of PK parameters across treatments will be based on the ratio of the geometric means (Test / Reference) and the 90% confidence interval about the ratio. No significant difference will be demonstrated if the 90% confidence intervals are fully contained within the limits of 80.00% to 125.00%.

QMD Ref: Worldwide-TMP-ST-006-4.0 Effective: 12Aug2019	Governing QMD: Worldwide-SOP-ST-001
Confidentiality Statement	

This document is the property of Worldwide Clinical Trials Inc. and may not be duplicated, copied, altered or removed from company without prior approval from Worldwide Quality Assurance or in compliance with Worldwide Standard Operating Procedures.

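### Section 4 selects 60 subjects under an 80% power target, but its own table needs 168 for AUC0-15/Dose, and the stated powers belong to a test that Section 6.11 does not use for its conclusions

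*SAP*

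**What the plan says.** SAP Section 4 takes the ratio and within-subject variability of early partial AUCs from a pilot study. It states that "Sample size calculations are based on the non-inferiority t-test for log-normal distributed data", for a two-treatment, two-sequence, two-period crossover, "using a target power of 80% and alpha level of 5" percent. It gives neither a non-inferiority margin nor the sidedness of alpha.

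The table has five rows, all per dose: AUC0-5, 0-10, 0-15, 0-20 and 0-30. The sample sizes are 48, 60, 168, 60 and 32, each with an expected power between 80.1% and 81.5%. The section ends: "Based on these findings a sample size of 60 subjects has been selected. For this study 68 subjects will be enrolled".

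Section 3.1 lists the partial AUCs "and during the first 30 minutes", including AUC0-15. Section 6.2.8 defines versions of Cmax, AUClast and AUCinf "adjusted for the nominal administered dose", but of no partial AUC. Section 6.11 compares the partial AUCs, AUC0-15 among them, without dose adjustment. It says: "Conclusions regarding the results of the statistical analysis (ANOVA) of PK parameters across treatments will be based on the ratio of the geometric means" and the 90% interval, with this rule: "No significant difference will be demonstrated if the 90% confidence intervals are fully contained within the limits of 80.00% to 125.00" percent.

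**The concern.** There are two gaps between the stated power and the design.

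First, the number 60 is presented as following from a table in which one of five rows needs 168. That row is not set aside, no partial AUC is named as the one that drives the size, and no reason for 60 is given. Each expected power is calculated at that row's own sample size, so every row appears to meet 80%. Power at 60 is shown only for the two rows whose required size is 60. The 60 and the 168 are both visible, but without a margin or sidedness the reader cannot turn the gap into a power.

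Second, Section 4 powers a non-inferiority test on dose-normalised exposure, whereas Section 6.11 concludes from an equivalence rule on exposure that is not dose-normalised. If the Section 4 powers do not apply to that rule, the SAP gives no support for the conclusion it plans to draw.

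**Working it through.** **Inputs.** GMR, intrasubject CV, sample size and power come from the Section 4 table. The decision limits come from Section 6.11. The doses (3 mg nalmefene hydrochloride IN; 1.0 mg nalmefene IM, given as 1.108 mg of the hydrochloride) come from Section 1.

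**Formulae.** For a 2x2 crossover on the log scale: s = sqrt(ln(1 + CV²)), SE = s·sqrt(2/N), df = N − 2, and noncentrality = (ln GMR − ln margin)/SE. Power is the probability that a noncentral t exceeds the one-sided critical value.

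**Step 1: recover the unstated margin and sidedness.** With one-sided 5%, solving each row's stated power for the margin gives 0.794 to 0.803, so 80% is implied. With one-sided 2.5% and an 80% margin, the required sizes would be 60, 74, 214, 78 and 40, and no row is reproduced.

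**Step 2: reproduce the table, then move to the chosen size** (80% margin, one-sided 5%).

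| Parameter, per dose | GMR % | CV % | N in table | Stated power % | Recomputed at table N % | N=60 % | N=68, all evaluable % |
|---|---|---|---|---|---|---|---|
| AUC0-5 | 149.40 | 178.15 | 48 | 81.0 | 81.0 | 88.2 | 91.5 |
| AUC0-10 | 127.06 | 129.21 | 60 | 81.1 | 81.1 | 81.1 | 85.3 |
| AUC0-15 | 108.76 | 159.69 | 168 | 80.1 | 80.1 | 43.3 | 47.2 |
| AUC0-20 | 125.68 | 127.97 | 60 | 81.0 | 79.9 | 79.9 | 84.2 |
| AUC0-30 | 123.57 | 74.40 | 32 | 81.5 | 82.0 | 97.1 | 98.4 |

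For AUC0-15/Dose: s = sqrt(ln(1 + 1.5969²)) = 1.1256. At N=60, SE = 1.1256·sqrt(2/60) = 0.2055 and the noncentrality is ln(1.0876/0.80)/0.2055 = 0.3071/0.2055 = 1.49. The critical t on 58 df is 1.672, which gives power of 43.3%.

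**Step 3: does the shortfall depend on the inferred margin?** Power for AUC0-15/Dose at N=60 is:
- 55.7% with a 75% margin, one-sided 5%;
- 32.3% with an 85% margin, one-sided 5%;
- 31.2% with an 80% margin, one-sided 2.5%.

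**Step 4: the Section 6.11 rule at N=60.** The rule passes only if the 90% interval lies inside ln 0.80 to ln 1.25, so its half-width must be below ln 1.25 = 0.223. At the planned CVs the half-width (1.672·SE) is 0.365, 0.302, 0.344, 0.301 and 0.203 for AUC0-5, 0-10, 0-15, 0-20 and 0-30. Four of the five intervals cannot fit at the planned CV. The probabilities of passing, integrated over the residual variance, are:
- with the table's GMRs and CVs: 0.00% for four rows (to two decimals) and 3.4% for AUC0-30;
- with a true ratio of exactly 100%: below 0.01% for four rows and 14.7% for AUC0-30;
- without dose adjustment: 0% for all five rows. The dose ratio is 3/1.108 = 2.71 on the hydrochloride basis or 3/1.0 = 3.0 nominally, so the planned ratios run from 108.76 × 2.71 ≈ 294% to 149.40 × 3.0 ≈ 448%.

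**The case against.** The table's arithmetic is sound, and Section 4 never claims that 60 gives 80% power for every row. The 168 is printed for anyone to see. Sizing on most of the rows can be a legitimate choice, and the margin and the reason for 60 may be in the protocol. The AUC0-15 inputs (GMR 108.76, CV 159.69) are out of line with their neighbours (127.06/129.21 and 125.68/127.97). With values midway between those, GMR 126.37 and CV 128.59, power at 60 would be 80.5%. The parameter list in Section 6.2.8 also omits AUC0-15. On the second gap, the two one-sided tests procedure contains the lower one-sided test, so non-inferiority at 80% could be read off the reported interval.

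Some of this stands. The 60 and 168 are disclosed, the AUC0-15 row may reflect an unstable pilot estimate, and the lower test is half of the planned procedure. But the SAP does not say it sized on a majority of rows, and it does not call the row unreliable. The omission from Section 6.2.8 carries no explanation and conflicts with Sections 3.1 and 6.11. Whatever the protocol holds, the SAP itself states the target, prints the table and draws 60 from it. Section 6.11 bases no conclusion on the lower limit alone. The 43% applies to the dose-normalised parameter and does not carry over to the unadjusted comparison; that is part of the mismatch between the sections.

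**Conclusion.** The concern holds. That 60 misses the 80% target for AUC0-15/Dose needs no assumption, because the SAP's own table asks for 168. The size of the miss, about 43% power at 60 and 47% at 68 if all are evaluable, rests on the inferred 80% margin and one-sided 5%. Under the alternatives tried, power at 60 lies between 31% and 56%. The other four rows are at or close to 80%, or above it. AUC0-20/Dose recomputes to 79.9% against the stated 81.0%, a small difference that is not a separate error.

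Section 4's powers also do not describe the Section 6.11 rule, which would almost never be met with Section 4's own inputs. This should be corrected. It is a matter of stating accurately what the design can show, and it does not mean the trial must be enlarged.

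**What to change.** In Section 4:

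1. State the margin and the sidedness of alpha that were used.
2. Give the power at N=60 for every row, in place of or beside the present column. If an 80% margin and one-sided 5% are confirmed, these are about 88, 81, 43, 80 and 97%. The sponsor should take them from its own calculation, so that the AUC0-20 figure agrees with the 81.0% already printed or the difference is explained.
3. Say that the 80% target is not met for AUC0-15/Dose, for which 168 would be needed, and give the reason 60 was chosen. If the reason is that the pilot estimate for this row is thought unreliable, say so.
4. Either align Section 6.11 with the non-inferiority test and dose-normalised partial AUCs used for sizing, or state that the Section 4 power does not apply to the Section 6.11 rule.

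Settle this before PK results are available, since a choice of test or parameter made later could be influenced by the data. Items 1 to 3 are wording in Section 4, and so is item 4 if a statement is enough. Aligning Section 6.11 needs a dated SAP amendment. No subjects are added. The cost is a less favourable stated power for AUC0-15/Dose.

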## 5 RANDOMIZATION

Subjects will be randomized to a sequence order of receipt of IN or IM doses after establishing eligibility and completing admission procedures. Subjects will be assigned to each of the 2 possible sequences.

The 2 sequences will be assigned as follows:

Sequence	Period 1	Period 2
I	Treatment A	Treatment B
II	Treatment B	Treatment A

## 6 PLANNED ANALYSES

No statistical analysis plan (SAP) prepared in advance of the data can be absolutely definitive and the final Clinical Study Report (CSR) may contain additional tables or statistical tests if warranted by the data obtained. The justification for any such additional analyses will be fully documented in the final CSR.

### 6.1 Analysis Populations

Subjects excluded from the Populations and the reason for their exclusion will be listed in [Appendix 16.2](#) of the CSR.

#### 6.1.1 Safety Population

The safety population will include all subjects who receive at least one administration of the study drugs.

#### 6.1.2 Pharmacokinetic Evaluation Population

The evaluable population will include all subjects who complete at least one treatment with all sampling time points taken to derive meaningful PK parameters. The PK population will be used for PK analysis. PK data for subjects who experience AEs (e.g. emesis) that may impact the PK results will be reviewed to assess the potential effect.

QMD Ref: Worldwide-TMP-ST-006-4.0 Effective: 12Aug2019	Governing QMD: Worldwide-SOP-ST-001
Confidentiality Statement	

This document is the property of Worldwide Clinical Trials Inc. and may not be duplicated, copied, altered or removed from company without prior approval from Worldwide Quality Assurance or in compliance with Worldwide Standard Operating Procedures.

Worldwide Clinical Trials Controlled Quality Management Document			
 WORLDWIDE CLINICAL TRIALS	Sponsor:	Opiant Pharmaceuticals	
	Protocol Number:	OPNT003-PK-001	

## 6.2 Derived Data

This section describes the derivations required for statistical analysis. Unless otherwise stated, variables derived in the source data will not be re-calculated.

### 6.2.1 Race

Where more than one race category has been selected for a subject, these race categories will be combined into a single category labeled “Multiple Race” in the summary tables. The listings will reflect the original selected categories.

### 6.2.2 Baseline

Baseline is defined as the last non-missing value (either scheduled, unscheduled or repeat) before the subject receives the first dose of study drug.

For variables that will be summarized by treatment, the Baseline for each period is defined as the last non-missing value (either scheduled, unscheduled or repeat) that is collected before dosing, but after check-in for the relevant period.

### 6.2.3 Early Terminations Assessments

Data collected during Early Termination assessments will be summarized alongside EOS procedures. All Early Termination data will be displayed as “Early Termination” in the listings, along with relevant Study Day.

### 6.2.4 Duration / Study Day / Time

Study day will be calculated as the number of days from first dose of study drug.

- date of event – date of first dose of study drug + 1, for events on or after first dose
- date of event – date of first dose of study drug, for events before first dose

### 6.2.5 Conventions for Missing and Partial Dates

It is not expected that there will be any missing dates, however in the rare case that an Adverse Event (AE) start date or time is missing and it is unclear whether the AE is treatment emergent or not then a conservative approach will be taken and it will be assumed that the AE occurred after first dosing.

All dates presented in the individual subject listings will be as recorded on the Electronic Case Report Form (eCRF).

QMD Ref: Worldwide-TMP-ST-006-4.0 Effective: 12Aug2019	Governing QMD: Worldwide-SOP-ST-001
Confidentiality Statement	

This document is the property of Worldwide Clinical Trials Inc. and may not be duplicated, copied, altered or removed from company without prior approval from Worldwide Quality Assurance or in compliance with Worldwide Standard Operating Procedures.

Worldwide Clinical Trials Controlled Quality Management Document			
 WORLDWIDE CLINICAL TRIALS	Sponsor:	Opiant Pharmaceuticals	
	Protocol Number:	OPNT003-PK-001	

## 6.2.6 Inexact Values

In the case where a safety laboratory variable is recorded as “> x”, “ $\geq$  x”, “ $<$  x” or “ $\leq$  x”, a value of x will be taken for analysis purposes.

## 6.2.7 Unscheduled Visits

Only scheduled post-baseline laboratory and vital signs values will be tabulated. Post-baseline repeat / unscheduled assessments will be disregarded, although these post-baseline assessments will be listed in the relevant appendices to the CSR.

## 6.2.8 PK Parameters

Concentration-time data will be analyzed using noncompartmental methods in Phoenix™ WinNonlin® (Version 8.1 or higher, Certara, L.P.) in conjunction with the internet-accessible implementation of Pharsight® Knowledgebase Server™ (PKSO; Version 4.0.4 or comparable product, Certara, L.P.). PKSO provides protected and structured storage, audit trails, and version control for study data, analyses, and related files, supporting 21 CFR Part 11 compliance.

During the PK analysis, concentrations below the limit of quantitation (BLQ) up to the time of the first quantifiable concentration will be treated as zero. Embedded (values between 2 quantifiable concentrations) and terminal BLQ concentrations will be treated as missing. PK analysis will be based on actual elapsed sample times, relative to time of dose.

The following PK parameters will be calculated:

$C_{\max}$	Maximum concentration, determined directly from individual concentration-time data
$C_{\max}/\text{Dose}$	$C_{\max}$ adjusted for the nominal administered dose
$T_{\max}$	Time to reach maximum concentration
$AUC_{0-2.5\text{min}}$	Area under the concentration-time curve from time-zero to 2.5 min; calculated using the linear trapezoidal rule allowing for extrapolation/interpolation to 2.5 min
$AUC_{0-5\text{min}}$	Area under the concentration-time curve from time-zero to 5 min; calculated using the linear trapezoidal rule allowing for extrapolation/interpolation to 5min
$AUC_{0-10\text{min}}$	Area under the concentration-time curve from time-zero to 10 min; calculated using the linear trapezoidal rule allowing for extrapolation/interpolation to 10min
$AUC_{0-20\text{ min}}$	Area under the concentration-time curve from time-zero to 20 min; calculated using the linear trapezoidal rule allowing for extrapolation/interpolation to 20min

QMD Ref: Worldwide-TMP-ST-006-4.0 Effective: 12Aug2019	Governing QMD: Worldwide-SOP-ST-001
Confidentiality Statement	
This document is the property of Worldwide Clinical Trials Inc. and may not be duplicated, copied, altered or removed from company without prior approval from Worldwide Quality Assurance or in compliance with Worldwide Standard Operating Procedures.	

Worldwide Clinical Trials Controlled Quality Management Document			
 WORLDWIDE CLINICAL TRIALS	Sponsor:	Opiant Pharmaceuticals	
	Protocol Number:	OPNT003-PK-001	

AUC 0-30min	Area under the concentration–time curve from time-zero to 30 min; calculated using the linear trapezoidal rule allowing for extrapolation/interpolation to 30min
AUC last (AUC 0-t )	Area under the concentration–time curve from time-zero to the time of the last quantifiable concentration; calculated using the linear trapezoidal rule
AUC last/Dose	AUC last adjusted for the nominal administered dose
AUC inf	Area under the concentration–time curve extrapolated to infinity, calculated as: $AUC_{inf} = AUC_{last} + C_{last}/\lambda_z,$ where $C_{last}$ is the last quantifiable concentration and $\lambda_z$ is the terminal elimination rate constant. The percentage of AUC inf based on extrapolation should be <30.0%
AUC inf/Dose	AUC inf adjusted for the nominal administered dose
AUC% Extrap	The percentage of AUC inf based on extrapolation, calculated as: $\%AUC_{Extrap} = (AUC_{inf} - AUC_{last})/AUC_{inf} * 100$
$\lambda_z$	The observed elimination rate constant ( $\lambda_z$ ); estimated by linear regression in the terminal phase of the log concentration-time profile; see additional criteria below
T 1/2	The observed terminal elimination half-life calculated as: $T_{1/2} = \ln(2)/\lambda_z$
C last	The last quantifiable concentration, determined directly from individual concentration-time data
T last	Time of the last quantifiable concentration
CL/F	Apparent total body clearance after extravascular administration, calculated as: $CL/F = Dose/AUC_{inf}$
Vz/F	Apparent volume of distribution following extravascular administration based on the terminal phase, calculated as: $Vz/F = Dose/(AUC_{inf} * \lambda_z)$
Fre l	Ratio of dose-adjusted AUC inf following IN administration of the test product relative to dose-adjusted AUC inf following IM administration of the reference product

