## Treatment A

## Treatment B

Footnotes describing each treatment will be provided in each output.

Treatment sequence labels will be displayed as follows:

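### The SAP describes the IM dose in two incompatible ways and leaves the chemical basis of Dose in Section 6.2.8 unstated, so Frel and the IN-to-IM scale of CL/F and Vz/F can carry a units error of 1.108

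*SAP*

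**What the plan says.** Section 1 defines Treatment A as a "3 mg nalmefene hydrochloride IN dose", given as one 0.1 mL spray of a 30 mg/mL solution. It defines Treatment B as "1.0 mg nalmefene IM dose (1.0 mL of 1.108 mg/mL nalmefene hydrochloride solution as a single dose in the gluteal muscle". The primary objective in Section 2 keeps the same pairing: "3mg nalmefene hydrochloride IN compared to a 1.0 mg dose of nalmefene administered IM". In both sections the IN dose is expressed as the salt and the IM dose as nalmefene.

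Section 9 differs. The titles of Tables 14.4.1, 14.4.2 and 14.4.3 and of Figures 14.4.1, 14.4.2 and 14.4.3 all express the IM dose as 1.0 mg of the hydrochloride.

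Section 6.2.8 defines Cmax/Dose, AUClast/Dose and AUCinf/Dose as the parameter "adjusted for the nominal administered dose". It computes CL/F as Dose/AUCinf and Vz/F as Dose/(AUCinf × λz). It defines Frel as the ratio of dose-adjusted AUCinf "following IN administration of the test product relative to dose-adjusted" AUCinf for the IM reference. No section says whether Dose is a quantity of hydrochloride or of nalmefene.

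CL/F and Vz/F are listed endpoints in Section 3.1 (for example "Volume of distribution (Vz/F) uncorrected for bioavailability (F"); Frel and the dose-adjusted parameters are not. Section 6.3 adds: "Footnotes describing each treatment will be provided in each output".

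**The concern.** The two descriptions of the IM dose cannot both be correct. On Section 1's own volume and concentration the IM injection contains 1.108 mg of hydrochloride; on the six titles it contains 1.0 mg. The titles head the main PK tables and figures, so the conflict would pass into the study report. A footnote worded as in Section 1 would then sit under a title that says something else.

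The second problem follows from the first. Every dose-normalised parameter needs a number for each treatment, and the rule offers only the nominal dose. Read literally against Section 1, the nominal figures are 3 and 1.0, but the first is milligrams of salt and the second milligrams of nalmefene. Dividing by these figures compares the two routes on different scales. The result is a fixed multiplicative error in the IN-to-IM comparison, which more subjects would not reduce. At stake are Frel, the relative size of CL/F and Vz/F between routes, and the labelling of the PK outputs.

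**Working it through.** **Doses from Section 1**

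- IN, as hydrochloride: 0.1 mL × 30 mg/mL = 3.0 mg. This reproduces the stated 3 mg.
- IM, as hydrochloride: 1.0 mL × 1.108 mg/mL = 1.108 mg, which Section 1 labels 1.0 mg of nalmefene. The document's own salt-to-nalmefene factor is therefore 1.108.
- IN, as nalmefene, by the same factor: 3 / 1.108 = 2.708 mg.

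**Formulas from Section 6.2.8**

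Let R = AUCinf(IN) / AUCinf(IM).

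- Frel = [AUCinf(IN) / D_IN] / [AUCinf(IM) / D_IM] = R × D_IM / D_IN.
- CL/F, IN relative to IM = (D_IN / D_IM) / R.
- Vz/F, IN relative to IM = the CL/F ratio × λz(IM) / λz(IN), so it has the same dose multiplier.

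**Dose multipliers**

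| Divisors (IN, IM) | Basis if Section 1 holds | D_IM / D_IN (Frel) | D_IN / D_IM (CL/F, Vz/F) |
|---|---|---|---|
| 3 and 1.108 | hydrochloride for both | 0.3693 | 2.708 |
| 2.708 and 1.0 | nalmefene for both | 0.3693 | 2.708 |
| 3 and 1.0 | mixed | 0.3333 | 3.000 |

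The first two rows agree, so the choice of basis does not matter for the comparison between routes as long as it is common to both. It does change the absolute values of CL/F and Vz/F.

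**Error from the mixed pair, if Section 1 holds**

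- Frel: 0.3333 / 0.3693 = 1 / 1.108 = 0.9025, that is 9.75% too low.
- CL/F and Vz/F, IN relative to IM: 3.000 / 2.708 = 1.108, that is 10.8% too high.
- Cmax/Dose, AUClast/Dose and AUCinf/Dose, IN relative to IM: the same 0.9025 as Frel.

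The factor does not depend on R. The SAP gives no value for R, so the following are assumed values for scale only:

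| Assumed R | Frel, one common basis (1.108R/3) | Frel, mixed pair (R/3) |
|---|---|---|
| 2.0 | 0.74 | 0.67 |
| 2.5 | 0.92 | 0.83 |
| 3.0 | 1.11 | 1.00 |

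**If the titles hold instead**, 3 and 1.0 are both milligrams of hydrochloride and that pair carries no error. Whether the literal divisors are right therefore depends on the contradiction that the SAP leaves open.

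**What the formal analysis uses.** The sentence in Section 6.11 that opens "Comparison of the log-transformed PK parameters" goes on to list Cmax, the partial AUCs, AUClast and AUCinf, none of them dose-adjusted. D_IN and D_IM do not enter those ratios or their 90% confidence intervals.

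**The case against.** The strongest reply is that nothing in the SAP is miscalculated. Volume times concentration gives the stated doses, Section 1 names the salt and the concentration, and a pharmacokineticist who notices this will use one basis and make no error. The protocol and the clarification letter on which the SAP says it is based may also fix the strength basis. The affected parameters are only summarised descriptively, and a wrong constant could be corrected later by rescaling.

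Much of this stands. The problem is an inconsistency and an undefined term, not a wrong sum, and the error is one the text permits and does not make inevitable. But the conflict between Section 1 and the titles lies within the SAP, which is the document that sets these derivations and titles. The literal reading of the nominal dose under Section 1 is the mixed pair, and the title of Table 14.4.2, which reports the parameters, also points to 1.0. Independent programming from the same text might repeat the error. The footnote clash is conditional, since the SAP does not prescribe the footnote wording.

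Three stronger readings are tempting and are not supported:

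- A reader might infer that Frel could equally be 10.8% too high. That would require accepting the titles' description and yet dividing by 1.108, a figure found only in the Section 1 description. That combination is contrived.
- A reader might infer that the primary comparison is biased. It is not, because its parameters are not dose-adjusted.
- A reader might infer that the sample size is affected, or that it is safe. Section 4 sizes the trial on pilot AUC/Dose ratios, but gives neither the pilot doses nor their chemical basis. The SAP supports neither conclusion, and none is drawn here.

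**Conclusion.** The point holds as an inconsistency, and the SAP is wrong as written: Sections 1 and 2 and six PK output titles cannot all describe the IM dose correctly, and Section 6.2.8 does not define the dose by which it divides. No view is taken on which description is right.

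The quantified error rests on two conditions: that Section 1 holds, and that the printed labels 3 and 1.0 are used as divisors. Frel is then multiplied by 0.9025 and the IN-to-IM ratios of CL/F and Vz/F by 1.108. With one basis common to both treatments and matching the reconciled dose, the error is zero.

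The consequence is limited to descriptive parameters, two of them Section 3.1 endpoints, and to the labels on the main PK outputs. It should be corrected before outputs are produced, but it does not threaten the formal comparison.

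**What to change.** Reconcile the dose description in Section 1 with the titles of Tables 14.4.1 to 14.4.3 and Figures 14.4.1 to 14.4.3, and word the treatment footnotes required by Section 6.3 the same way. Add one sentence to Section 6.2.8 stating a single chemical basis for Dose (hydrochloride or nalmefene), the same for both treatments, with the two numerical values taken from the reconciled description. It should apply to Cmax/Dose, AUClast/Dose, AUCinf/Dose, Frel, CL/F and Vz/F.

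The cost is that one sentence and the reconciled wording. No data collection, trial conduct or formal analysis changes.
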